## 7. DATA MANAGEMENT METHODS

All data collected for this study will be part of the case report forms (CRFs) originally designed for the main trial protocol MALARIA-094. Samples will be tracked using the LIMS system in the Broad Genomics Platform; raw and filtered data will be stored in a Structured Query Language (SQL) database on a secure Broad server with user permissions restricted to designated study personnel. The clinical data management system will be overseen by GSK. Exchanges of clinical and genetic data will be performed according to a mutually agreed schedule and terms.

## 8. PROTECTION OF HUMAN RESEARCH SUBJECTS

No analysis of human DNA will be performed in this study. Samples will be collected exclusively for parasite genotyping. Therefore, this study will not result in any risks, legal or ethical concerns for subjects other than the ones discussed in the original study protocol (MALARIA-094). Subjects' discontinuation of the study will also follow procedures specified in the main protocol. Informed consent for the genotyping study will be included in the informed consent of the main protocol.

“The cumulative distribution functions will be estimated in two ways: first, by stratifying by study site using the Kaplan-Meier estimator, and second, by adjusting for other baseline participant characteristics via targeted maximum likelihood estimation (TMLE, Moore and van der Laan, 2009).”

as

“The cumulative distribution functions will be estimated in two ways: first, by using the Nelson-Aalen estimator for the cumulative hazard function, and

second, by adjusting for other baseline participant characteristics via targeted maximum likelihood estimation (TMLE, Moore and van der Laan, 2009)."

The Kaplan-Meier estimator was replaced with the Nelson-Aalen estimator because the simultaneous confidence band program is available for the Nelson-Aalen estimator only. This program does not accommodate stratification, therefore an unstratified estimator is considered, which matches the kernel-smoothed estimation of instantaneous hazard functions and their contrasts, which is also unstratified.

- Section 7.5: In the last paragraph, revised the sentence

"These analyses will be done for each individual and pair of study groups specified in Tables 2, 3, and 4, except the analyses comparing active vaccine study groups and using the control group for bias-correction from possible secular trends will not be done (i.e., comparisons denoted by asterisks in Tables 2, 3, 4)."

as

"These analyses will be done for each individual and pair of study groups specified in Table 5, analogously to the analysis of instantaneous kernel-smoothed hazard functions and their contrasts."

Date: April 4, 2022

SAP version: 1.2

Modifications:

- Added Section 9 on post-hoc exploratory analyses.

Date: October 24, 2022

SAP version: 1.3

Modifications:

- Added Section 5.1.1.1 describing the modified post-hoc definition of molecular parasite positivity for application in Month 32 analyses.
- Added the statement

"All analyses using follow-up through Month 32 will use the modified post-hoc definition of molecular parasite positivity as described in Section 5.1.1.1."

at the beginning of Section 7.7 to reiterate the difference in the SAP-specified

read threshold for molecular parasite positivity in analyses through Month 20 vs. Month 32 of follow-up.

Date: March 8, 2023

SAP version: 1.4

Modifications:

- Added Section 9.1 on sensitivity of overall VE estimates to the read count threshold for parasite positivity.
- Added Section 9.4 on the post-hoc analysis of modification of RTS,S vaccine efficacy by baseline parasite positivity.

Date: April 7, 2023

SAP version: 1.5

Modifications:

- Section 8: Revised the comparison of all active arms pooled vs. control to be active arms GP2–GP4 vs. control in all ATP sieve analyses in pursuit of exploratory objective 1.
- Section 8.4.2: Clarified one- vs. two-sided hypothesis testing and statistical significance in the following statements:

“For the binary haplotype-level features in (a)–(c), we will estimate genotype-specific hazard-ratio (relative) VE with 95% CIs and a two-sided test for differential genotype-specific (relative) VE using...”

“One-sided testing will be performed for comparisons to the control GP1 regimen of 3D7 Hamming distances, and two-sided testing will be performed for head-to-head RTS,S regimen comparisons of 3D7 Hamming distances as well as for all comparisons of all other quantitative sequence features. Statistical significance is defined as in Section 7.8 except, for multiplicity sets in which one-sided testing is performed, the same definition of FWER and FDR statistical significance is applied to doubled one-sided p-values.”

- Added Section 8.4.3 specifying hypothesis testing multiplicity sets considered in the sieve analysis for primary endpoint 1.

Date: July 31, 2023

SAP version: 1.6

Modifications:

- Revised Section 9.4 to formalize and align statistical analyses with the separate scientific questions about baseline parasite positivity and month 2 force of infection (M2-FOI) as potential VE modifiers of interest.
- Added Section 9.4.2.3 describing a sensitivity analysis to unmeasured confounding.

Date: August 25, 2023

SAP version: 1.7

Modifications:

- Added in Section 9.4 the indicator of the onset of antimalarial drug treatment between the first vaccination and the month 2 scheduled visit as an additional adjustment covariate in the Cox models to control for potential confounding.

CONTENTS

SAP MODIFICATION HISTORY	2
1 SYNOPSIS	8
2 RANDOMIZED TREATMENT ARMS	9
3 STUDY COHORTS.....	11
4 OBJECTIVES	12
4.1 Context for MAL-095 Objectives Relative to MAL-094 Parent Protocol Objectives.....	12
4.2 Primary Objective.....	12
4.3 Exploratory Objectives	13
5 STUDY ENDPOINTS.....	13
5.1 Primary Endpoints.....	13
5.1.1 Definition of New Malaria Infection	13
5.1.1.1 Modified Definition of Molecular Parasite Positivity for Month 32 Analyses 15	
5.1.2 Definition of Primary Endpoint 1	15

1 SYNOPSIS

The goal of the amplicon sequencing and genotyping study (hereafter referred to as 'genotyping study') is to assess vaccine efficacy against molecularly confirmed malaria infection using ultra-sensitive molecular amplification and sequencing methodology to detect *Plasmodium falciparum* (*P. falciparum*) parasites from serial blood samples to be collected from children immunized with the primary and yearly booster immunizations of the RTS,S/AS01E vaccine as part of their participation in Protocol MALARIA-094 (MAL-094). Genomic analysis will be performed on parasites from blood spot samples collected from children aged 5-17 months when first immunized with RTS,S/AS01E on different dosage and schedule regimens under the MAL-094 clinical study parent protocol (Study Number 204889), entitled "Efficacy, safety and immunogenicity study of GSK Biologicals' candidate malaria vaccine (SB257049) evaluating schedules with or without fractional doses, early dose 4 and yearly doses, in children 5-17 months of age."

The MAL-094 study, being conducted at the Agogo, Ghana and Siaya, Kenya study sites in East and West Africa, assesses proof of concept for a fractional (Fx) dose schedule under conditions of natural exposure. The study also assesses the role of third dose spacing in a Fx dose schedule, the effect of an earlier full fourth dose at Month 14, and the effect of multiple Fx versus full yearly doses. The study is conducted in children 5-17 months of age at first vaccination living in areas of moderate to high malaria transmission. In addition to assessing vaccine efficacy against clinical malaria disease, this study will for the first time assess vaccine efficacy against asymptomatic and submicroscopic parasitemia in dried blood spots collected in monthly surveys from every child enrolled in this study using ultra-sensitive molecular genotyping methods. A full description of the design and sampling methodology is described in the MAL-094 trial protocol.

In the present MAL-095 study, samples generated by the MAL-094 trial are used in combination with cutting-edge genomic and statistical analysis to generate a better understanding of the RTS,S/AS01E vaccine. Whereas traditional PCR-based infection screens yield a simple binary outcome of positive or negative infection status, amplicon sequencing data provide information on the complexity of infection (COI), a measure of the number of genetically distinct parasite lineages in each participant sample in the trial, and can be used to estimate the rate at which new infections occur and parasite lineages turn over. The resulting data yield not only the infection status of each participant, but also information on the incidence rates of new malaria infection. These

data allow assessment of VE of each vaccine study arm to prevent new genetically distinct malaria infection.

In addition to supporting the primary objective of evaluating differences in overall VE against new malaria infection among the arms of the MAL-094 trial, amplicon sequencing data enable investigations into the nature of immunity generated by vaccination and natural disease exposure. The longitudinal sampling design allows for exploration of whether and how prior infection history impacts participants' susceptibility to new infections. There will also be assessment of the degree to which allele-specific protection contributes to overall VE, and how VE depends on genetic distance of infecting parasites to the vaccine strain, as performed in the MALARIA-055 ancillary genotyping study (Benkeser, Juraska, and Gilbert, 2018).

The design of the MAL-094 trial, in combination with the unique data generation capacity developed at the Broad Institute for previous RTS,S work, creates an opportunity to significantly improve the efficacy and understanding of RTS,S/AS01_E vaccination, and to investigate the dynamics of naturally acquired immunity to malaria infection.

Enrollment of MAL-094 began on October 16, 2017 in Agogo and on May 18, 2018 in Siaya. Enrollment was completed at Agogo on February 6, 2018 and on September 25, 2018 in Siaya. The two planned MAL-095 data analyses will be conducted after all enrolled participants reach the Month 20 visit (which occurred in June, 2020) and after all enrolled participants reach the Month 32 visit (which is estimated to occur in July, 2021).

Given similarities in the molecular data generation and statistical approaches between this project and the ancillary genotyping study performed for the phase 3 MALARIA-055 study (MALARIA-066), there is confidence to perform the necessary data generation and analyses to accomplish the study objectives.

2 RANDOMIZED TREATMENT ARMS

This study is an ancillary study of the GlaxoSmithKline (GSK) RTS,S/AS01E Phase IIb randomized trial (Study Number 204889) that is performed across both study sites Agogo and Siaya. The original randomized trial (MAL-094) vaccinates approximately 1,500 subjects 5-17 months of age in multi-centers according to the following groups:

(GP1) Control group, i.e., rabies vaccine at Month 0, Month 1, Month 2;

(GP2) Group R012-20 - a course of RTS,S/AS01E full dose at Month 0, Month 1, Month 2, and a full dose at Month 20;

[figure not shown]
(GP3) Group R012-14-mD - a course of RTS,S/AS01E full dose at Month 0, Month 1, Month 2, and yearly full doses at Month 14, Month 26, Month 38;

(GP4) Fractionated (Fx) Group Fx012-14-mFxD - a course of RTS,S/AS01E full dose at Month 0 and Month 1, followed by RTS,S/AS01E 1/5th dose at Month 2, Month 14, Month 26, and Month 38.

(GP5) Group Fx017-mFxD - a course of RTS,S/AS01E full dose at Month 0 and Month 1, followed by RTS,S/AS01E 1/5th dose at Month 7, Month 20, and Month 32.

A total of 300 subjects are randomly allocated to each treatment group (Figure 1 below from the MAL-094 protocol).

Figure 1. MAL-094 protocol describing study arms and study visits

3 STUDY COHORTS

Analyses will be conducted in two distinct study cohorts:

(Cohort 1) The According-To-Protocol (ATP) cohort includes all participants who received the first three vaccinations according to the MAL-094 protocol procedures and who are observed to be at risk for a molecularly confirmed malaria infection at 14 days post-Dose 3.

(Cohort 2) The Total Vaccinated Cohort (TVC) is all participants who received at least one dose of a study vaccine.

Primary and exploratory analyses of vaccine efficacy will be conducted both in ATP and TVC cohorts, with participants analyzed according to the as-treated principle (i.e., actually received treatments). The same ATP cohort will be analyzed in vaccine efficacy analyses of both primary study endpoints defined in Sections 5.1.4 and 5.1.5.

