For analyses of the ATP cohort, for both primary endpoints, the comparator group (rabies control vaccination) window of follow-up for capturing outcomes differs depending on the vaccine group to which it is compared. In particular, the primary objectives in the ATP cohort study primary endpoints occurring after 14 days post-Dose 3 through to the visit scheduled 12 months post-Dose 3 (Month 14 for Groups 2, 3, 4 and Month 19 for Group 5), such that the follow-up period for registering events is Month 2.5-14 for each of Groups 2, 3, 4 vs. Control and is Month 7.5-19 for Group 5 vs. Control (the first row of Table 1 describes all of these follow-up periods).

For comparing the vaccine study groups head-to-head, all pairwise comparisons for the TVC analyses use a follow-up period starting from first vaccination through to the Month 20 study visit, as for the analyses of each RTS,S/AS01E vaccine arm vs. control. The ATP cohort analyses for these pairwise study group comparisons use a follow-up period of 11.5 months starting at 14 days post-Dose 3 (Table 1).

Table 1. Follow-up Intervals (in Months) Since First Vaccination for Counting New Malaria Infections for the Primary Analyses in the ATP Cohort (Each Entry is for the Comparison of Two Study Arms, where 2.5 indicates 14 days post Dose 3 in Groups 1-4, 7.5 indicates 14 days post Dose 3 in Group 5, 14 indicates the Month 14 study visit, and 19 indicates the Month 19 Study Visit)*

	GP2 R012-20**	GP3 R012-14**	GP4 Fx012-14	GP5 Fx017
GP1 Cont.	2.5-14 vs. 2.5-14		2.5-14 vs. 2.5-14	7.5-19 vs. 7.5-19
GP2 R012-20			2.5-14 vs. 2.5-14	2.5-14 vs. 7.5-19
GP3 R012-14				2.5-14 vs. 7.5-19
GP4 Fx012-14				2.5-14 vs. 7.5-19

*“Study visit” refers to a monthly longitudinal sampling visit through Month 20.

**GP2 and GP3 are pooled for comparison with GP1 over 2.5-14 months given GP2 and GP3 are identical during this follow-up period. Similarly, GP2 and GP3 are pooled for comparison with GP4 during 2.5-14 months and are pooled for comparison with GP5 (2.5-14 months for GP2 and GP3 vs. 7.5-19 months for GP5).

Table 2 lists the set of primary vaccine efficacy and relative vaccine efficacy analyses that are done, with follow-up periods, and grouping the analyses into three sets (vs. control, vs. the standard R012-20 vaccine regimen, and head-to-head novel vaccine regimens).

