For the ATP analyses, differences in prognostic factors for molecular detection of new malaria infection could arise between the analyzed groups because the analyses are restricted to subgroups defined by the post-randomization variable of qualifying for the ATP cohort at Month 2.5 or Month 7.5 (Horne et al., 2001; Gilbert et al., 2013). In particular, a needed assumption for the ATP cohort analyses to assess causal effects of vaccination is that there are no unmeasured/unaccounted for baseline covariates that predict both ATP qualification status and the outcome type under study. Therefore, in preparation for the proportional hazard analyses, we will first study if there exist measured baseline covariates other than study site and ATP Propensity Score (described below) that are dual predictors of ATP status and either outcome type. If affirmative evidence is uncovered, such predictors will be adjusted for in every ATP cohort analysis, along with study site and ATP Propensity Score (if it is found to be predictive of the ATP status).

The following approach will be used to assess this evidence. Super Learner will be conducted to predict status of qualifying for the ATP from all available baseline covariates, using negative log-likelihood loss and 10-fold cross-validation. A simple parametric library of learners from the *SuperLearner* or *sL3* R packages will be used, for example, logistic regression that considers all possible two-way interactions from among the baseline covariates listed in Section 6.2 and that selects the best model based on stepwise model selection. If the classification accuracy is clearly greater than

expected from random noise, based on the 95% confidence interval for the cross-validated area under the ROC curve exceeding 0.5, then an ATP Propensity Score will be defined as the logit transformed Super Learner model fitted probabilities of being ATP, and all ATP cohort analyses of primary endpoint 1 will adjust for the ATP propensity score. The statistical analyses will use the nonparametric bootstrap for producing confidence intervals and p-values, to account for the fact that the propensity score is estimated. Depending on the number of variables that may be predictive of ATP qualification, we may consider more flexible methods for modeling the ATP propensity score, such as the highly adaptive lasso.

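### The ATP comparison of Group 5 with control over Month 7.5–19 qualifies the two arms five months apart, and nothing in these documents re-qualifies controls when follow-up opens

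*SAP*

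**What the plan says.** SAP Section 3 sets two conditions for the ATP cohort. It "includes all participants who received the first three vaccinations according to the MAL-094 protocol procedures", and it takes those "who are observed to be at risk for a molecularly confirmed malaria infection at 14 days post-Dose 3". No comparison-specific version is defined: "The same ATP cohort will be analyzed in vaccine efficacy analyses of both primary study endpoints".

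The third dose falls at different times. SAP Section 2 gives "Control group, i.e., rabies vaccine at Month 0, Month 1, Month 2", while Group 5 has full doses at Months 0 and 1 "followed by RTS,S/AS01E 1/5th dose at Month 7, Month 20, and Month 32". The caption of Table 1 (SAP 5.1.4) carries this into the time axis: "where 2.5 indicates 14 days post Dose 3 in Groups 1-4, 7.5 indicates 14 days post Dose 3 in Group 5". For Group 5 against control, Tables 1 and 2 count events over Month 7.5–19 in both arms.

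SAP 7.5 recognises that ATP analyses are "restricted to subgroups defined by the post-randomization variable of qualifying for the ATP cohort at Month 2.5 or Month 7.5". Its answer is to search for baseline predictors of both ATP status and outcome, and to fit an ATP propensity score from baseline covariates. The score is used only if the confidence interval for its cross-validated AUC exceeds 0.5. SAP 6.2 lists site, age and sex as the baseline variables.

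SAP 7.1 and 7.8 make Group 5 against control one of two comparisons of primary interest, tested at 0.05 without multiplicity adjustment.

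**The concern.** In this contrast one arm is selected at the moment follow-up opens and the other five months before. A Group 5 child who is still followed but misses the Month 7 dose, or receives it outside protocol procedures, leaves the cohort. A control child with the same history around Month 7 stays. If such children differ in infection risk, the hazard ratio mixes the vaccine effect with whatever drives Month 7 qualification: illness, recent infection, treatment or attendance. These arise after baseline, so a baseline-covariate score does not capture them. The score also gives no means of applying to controls a Month 7 condition they never faced.

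Two further gaps follow.

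- **Start date.** Endpoint 1 in the ATP cohort runs from 14 days after Dose 3 (SAP 5.1.4). For a control analysed from Month 7.5 that is not the child's own Dose 3 date, and the SAP does not say which date replaces it.
- **Endpoint 2.** A control lost between Months 2.5 and 7.5 remains in the cohort with a missing outcome. With no tests in the window, the auxiliary outcome of SAP 7.6.1 is set to 0. A Group 5 child lost over the same months is not in the cohort.

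The estimate is used again. SAP 7.5 divides the Group 5 hazard ratio against control by that of Groups 2+3 against control, and Table 2 marks Group 5 against Group 4 for the same control correction. Windows opening at Month 7.5 recur in Tables 3, 4 and 5.

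**Working it through.** **1. The plan's own interval.** SAP 5.1.4 states 11.5 months of follow-up. 14 − 2.5 = 11.5 and 19 − 7.5 = 11.5, so it reproduces. Window lengths match; qualification times do not.

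**2. Gap between qualifying and starting follow-up, Group 5 against control.**

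| Arm | Dose 3 | Qualifies | Window opens | Gap (months) |
|---|---|---|---|---|
| Group 5 | Month 7 | 7.5 | 7.5 | 0 |
| Control | Month 2 | 2.5 | 7.5 | 7.5 − 2.5 = 5.0 |

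Groups 2, 3 and 4 against control all have Dose 3 at Month 2 and a window opening at 2.5, so their gap is 0 in both arms.

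**3. What the gap could do to VE.** Let q be the share of controls followed at Month 7.5 who would have failed the Month 7 criterion, and r their infection hazard relative to other controls. Neither is in the documents; both are assumed. Ignoring any other selection:

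apparent HR = true HR / (1 − q + q·r)

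With true VE 30% (HR 0.70):

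| q | r | 1 − q + q·r | Apparent HR | Apparent VE |
|---|---|---|---|---|
| 5% | 1.3 | 1.015 | 0.690 | 31.0% |
| 10% | 1.5 | 1.050 | 0.667 | 33.3% |
| 15% | 1.5 | 1.075 | 0.651 | 34.9% |
| 15% | 0.7 | 0.955 | 0.733 | 26.7% |

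With r = 1, or with entry aligned, the divisor is 1 and nothing changes. The formula takes average hazards at the start of the window. When most children become infected, high-risk children leave the risk set first, so it is only approximate for a Cox estimate over the full window.

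**4. The opposite screen.** Controls must also have a per-protocol Month 2 dose, which Group 5 never receives. Suppose a share s of Group 5 would have failed such a screen, with relative hazard u. The multiplier on the true HR becomes (1 − s + s·u) / (1 − q + q·r). With s = q = 5% and u = r = 1.5 it is 1.025 / 1.025 = 1, and the two effects cancel. The sign of the net bias is therefore not fixed.

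**5. Carry-over.** In the bridged comparison, HR(Group 5 vs Groups 2+3) = HR(Group 5 vs control) / HR(Groups 2+3 vs control). Any factor on the numerator passes through unchanged, because the denominator lacks this timing gap.

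**The case against.** The best counter-arguments are these.

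- **The detailed criteria lie elsewhere.** SAP Section 3 and Protocol 3.3.1–3.3.2 defer to the MAL-094 protocol, which is not available here. A Month 7 rule for controls there cannot be excluded. This stands as a caveat; none appears in these documents.
- **Loss to follow-up is largely aligned for endpoint 1.** A control lost before Month 7.5 contributes no person-time. This stands: for endpoint 1 the problem is confined to children still followed. For endpoint 2 the TMLE models the missing outcome, which mitigates the issue but leaves the two arms' cohorts defined differently.
- **The plan discloses ATP selection and has a co-primary check.** SAP 7.5 states the identifying assumption, and the TVC comparison over Month 0–20 (SAP 4.2, Table 2) keeps children whatever doses they received. This stands, although that check covers a different window.
- **The possible shift is small beside sampling error.** Assume 250 children per arm and 60–80% of controls infected. The 95% interval around a VE of 30% is then about 11–45% to 14–43%, against shifts of about 1 to 5 points. This argues for a modest remedy; it does not remove the mismatch.

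Stronger readings are tempting but unsupported. A reader might infer from the 45.3% in SAP 8.5.1 that Month 7 failures are frequent. That figure is right-censoring under a rule of two consecutive missed visits, arms pooled, for the exploratory recurrent-event models. The SAP adopted the three-visit rule (29.5%), and neither figure measures Month 7 dosing or attendance. Nor does the parent trial's planning figure of 250 evaluable of 300 (50/300 = 16.7% not evaluable), which covers every reason for non-evaluability. A reader might also infer that only Group 5 is selected, or that VE must be inflated. Step 4 and the last row of step 3 show otherwise.

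**Conclusion.** The mismatch holds on the SAP text. In every ATP contrast of Group 5 with control, Group 5 is qualified on a Month 7 dose at the start of follow-up, control on a Month 2 dose five months earlier, and no stated rule re-qualifies controls. The planned covariate score does not address it. Direction and size cannot be determined from the documents. Under assumed q of 5–15% and r of 0.7–1.5, with the opposite Month 2 screen ignored, a true VE of 30% would appear as about 27% to 35%. The point matters because the comparison is of primary interest, is tested without adjustment, and enters the bridged comparisons. It does not touch the TVC analysis or the ATP comparisons among Groups 1–4, and it does not show that the ATP result is wrong. It would fall away if MAL-094 applies a matching Month 7 rule to controls.

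**What to change.** Leave the primary ATP cohort as it is. SAP v1.7 post-dates inspection of Month 20 data (SAP 5.1.1.1), so replacing the cohort now would be a post-hoc change to a primary analysis. Instead, for every ATP window opening at Month 7.5, including model (1) of the bridged analyses:

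1. State the control's start date: 14 days after the actual Month 7 visit. Add a rule for controls who missed it; SAP 7.6.1 already falls back on the target date for a missed visit.
2. Report a labelled sensitivity analysis in which controls must also have an in-window Month 7 visit and still be in follow-up 14 days later.
3. Report a second labelled analysis of all Group 5 and control children under follow-up at Month 7.5, regardless of the Month 7 dose and with no dosing criterion in either arm. This removes both dosing screens, though it answers a different question and still conditions on remaining in follow-up.
4. Tabulate, by arm, how many children in follow-up at Month 7.5 meet and fail each criterion. This shows q for Group 5 directly.

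All arms have monthly sampling visits through Month 20, so the cost is SAP wording, cohort flags and two extra model runs. The matched analysis has slightly fewer controls. It mirrors per-protocol dosing only in part, because reasons for not dosing a child who attended at Month 7 have no counterpart in control, and it leaves the Month 2 screen in place.
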